10. REFERENCES

LIST OF ABBREVIATIONS AND RELEVANT DEFINITIONS

ABR	ABR form, General Assessment and Registration form, is the application form that is required for submission to the accredited Ethics Committee (In Dutch, ABR = Algemene Beoordeling en Registratie)
AE	Adverse Event
CB-CT	Cone beam computed tomography
CCMO	Central Committee on Research Involving Human Subjects; in Dutch: Centrale Commissie Mensgebonden Onderzoek
CI	Cochlear implant
CO	Cochleostomy approach
CV	Curriculum Vitae
CVC	Consonant-Vowel-Consonant, dutch speech perception test
eCAP	Evoked compound action potential
ECochG	Intracochlear electrocochleography
EU	European Union
GCP	Good Clinical Practice
IC	Informed Consent
LW	Lateral wall electrode array
METC	Medical research ethics committee (MREC); in Dutch: medisch ethische toetsing commissie (METC)
MPT	Mastoidectomy-posterior tympanotomy
PTA	Pure tone audiometry
PM	Perimodiolar electrode array
RW	Round window approach
(S)AE	(Serious) Adverse Event
Sponsor	The sponsor is the party that commissions the organisation or performance of the research, for example a pharmaceutical company, academic hospital, scientific organisation or investigator. A party that provides funding for a study but does not commission it is not regarded as the sponsor, but referred to as a subsidising party.
SRT	Speech Reception Threshold
SNHL	Sensorineural hearing loss
Wbp	Personal Data Protection Act (in Dutch: Wet Bescherming Persoonsgevens)
WMO	Medical Research Involving Human Subjects Act (in Dutch: Wet Medisch-wetenschappelijk Onderzoek met Mensen)

SUMMARY

Rationale: In order to preserve the residual hearing in patients with sensorineural hearing loss (SNHL) receiving a cochlear implant (CI), the insertion trauma to the delicate and microscopic structures of the cochlea needs to be minimized. The surgical procedure starts with the conventional mastoidectomy-posterior tympanotomy (MPT) approach to the middle ear, and is followed by accessing the cochlea, with either a cochleostomy (CO) or via the round window (RW). Both techniques have their benefits and disadvantages. Another aspect is the design of the electrode array. There are fundamentally two different designs: a 'straight' lateral wall lying electrode array (LW), or a 'pre-curved' perimodiolar cochlear lying electrode array (PM). Interestingly, until now, the best surgical approach and type of implant is unknown. Our hypothesis is that the combination of a RW approach and a LW lying electrode array minimizes insertion trauma, leading to better hearing outcome for SNHL patients.

Objective: Comparison of hearing preservation and outcome of two fundamentally different cochlear implants designs (LW or PM) and the two most used surgical approaches (RW or CO). Secondly, asses the structure preservation (i.e., scalar position) of each combination of electrode design/surgical approach. Thirdly, find objective electrophysiological measures for insertion trauma.

Study population: A total of 48 patients with severe SNHL, age ≥ 18 years, who meet the in/exclusion criteria used for cochlear implantation.

Study design: Randomized controlled single-blind trial consisting of four groups: 1: RW and LW, 2: CO and LW, 3: RW and PM and 4: CO and PM.

Intervention: Randomization to one of the four groups.

Main study parameters/endpoints: Primary outcome: Pre- and postoperative hearing thresholds of (low frequency) pure tone audiometry (LF-PTA), secondary outcomes: scalar position of the electrode array, ECochG measures and speech perception score.

Nature and extent of the burden and risks associated with participation, benefit and group relatedness: Cochlear implantation by way of a cochleostomy or round window approach, using different electrode array types, is the standard medical care for patients with severe bilateral hearing loss, as it is a relative simple and low-risk procedure that greatly benefits the patients. Cone-beam CT (CB-CT) imaging postoperatively leads to exposure of low-dose radiation (effective dose: 0.18 mSv), and is therefore considered to be of low-risk.

1. INTRODUCTION AND RATIONALE

In people with severe hearing loss or deafness, hearing can be (partially) restored with a cochlear implant (CI). A cochlear implant bypasses the hair cells and directly stimulates via electrical impulses the auditory nerve, allowing patients with non-functioning hair cells to hear again. Cochlear implantation for severely hearing impaired patients has become a standard and accepted treatment throughout the years in high income countries. A tremendous development in auditory perception with a CI has been achieved since first implantations in the 1980s, from only sound detection to speech understanding (Eshraghi et al., 2012). However, speech understanding is not yet optimal, especially in difficult situations where background noise is present. Several studies have shown that preserving residual hearing can lead to better hearing outcomes, especially in noisy environments (Skarzynski et al., 2014; Gifford et al., 2013; Buechner et al., 2008; Gfeller et al., 2006). In order to preserve residual hearing, insertion trauma to the delicate structures of the cochlea needs to be minimized, by making the surgical implantation procedure as minimally invasive as possible. Therefore, we consider the various possible surgical approaches. The surgical procedure commonly starts with the conventional mastoidectomy-posterior tympanotomy (MPT) approach to the middle ear, and is followed by accessing the cochlea, with either a cochleostomy (CO) or via the round window (RW). Several papers including systematic reviews comparing CO and RW approaches in literature, concluded that evidence lacks to show preference for one or the other approach with respect to hearing preservation (Havenith et al., 2013, Wanna et al., 2014, Wanna et al., 2015, Fan et al., 2018, Snels et al., 2019). Both techniques of accessing the cochlea have their pros and cons (e.g. cochleostomy leads to better angle of insertion, while RW approach ensures correct localization of the implant and leaving the integrity of the anatomical structures intact). One may also argue a preference for a certain approach based on individual cochlear structures. Several studies have clearly shown that each human cochlea has a different micro-anatomy in parallel with one's unique fingerprint (Avci et al., 2017, Escude et al., 2006, Rask-Andersen et al., 2011).

Another aspect relevant for minimizing insertion trauma, is the design of the electrode array. There are two fundamentally different designs: a 'straight' lateral wall lying electrode array (LW), or a 'pre-curved' perimodiolar lying electrode array (PM). No evidence has been provided that one design outperforms the other in terms of hearing outcome and structure preservation (Wanna et al., 2014, Snels et al., 2019, Holden et al., 2013). On the one hand, lateral wall positioning might be the best way to preserve the microscopical structures (spiral/osseous ligament, basilar membrane, lateral wall, see **fig. 1**); on the other hand, perimodiolar positioning might provide better hearing outcome (which is the ultimate objective for deaf

patients with a CI), as the electrodes are situated close to the spiral ganglion cells to be stimulated. Also, the perimodiolar electrode might not touch the lateral wall if inserted correctly, leading to preservation of the microanatomy of the intracochlear structures. Speech performances scores were better for the LW group, also if the scalar translocations were accounted for in the PM group (O'Connell 2016). While other studies report better outcomes for speech performance for the PM group (Holden et al., 2013, Wanna et al., 2014). The majority of the studies, however, show no difference between both groups (van der Jagt et al., 2016, van der Marel et al., 2015, Fabie et al., 2018, Moran et al., 2019, Doshi et al., 2015). However, all these studies had a high risk of bias. In addition, they did not differentiate between the surgical approaches, which induces a major confounding factor.

It is unclear which surgical approach and electrode design is most suited to achieve minimal insertion trauma, and thereby preserving the residual hearing in cochlear implantation surgery. Therefore, it is not surprising that worldwide both type of approaches and electrode designs are used.

Considering the surgical approach and electrode array design, it is important to note that during insertion no reliable feedback is provided, regarding the array tip position in relation to the intracochlear structures. After inserting the tip of the electrode array in the round window perforation or cochleostomy, only tactile feedback is available, which might not be sufficient to know whether the implant is correctly inserted. Correct insertion, for both cochleostomy and round window approach, ensures that the implant is in the scala tympani of the cochlea. If during insertion, the CI translocates to the scala vestibuli or scala media, the basilar membrane with the organ of Corti (the actual hearing receptor organ) is damaged (see **fig. 1**). Scalar translocation negatively influences the final hearing outcome and hearing preservation for CI patients (Holden et al., 2013, Shaul et al., 2018).

One of the possibilities to view the intracochlear structures and thereby asses the scalar location of the CI (thus providing postoperative feedback), is by applying imaging techniques after surgery such as cone beam computed tomography (CB-CT) (see **fig. 2**), which has been proven to be suitable in detecting the scalar position of the electrode array (Zou et al., 2015, Saeed et al., 2014, Mosnier et al., 2017). Another possibility to detect insertion trauma is the intraoperative, intracochlear electrocochleography (ECochG) which measures responses of residual functioning hair cells to acoustic tone stimuli. During insertion, ECochG measures can be used to assess insertion trauma, providing feedback of the insertion (Choudhury et al., 2012, Dalbert et al., 2015b, Giardina et al., 2019, Fontenot et al., 2019).

Our first aim is to compare the hearing preservation in CI recipients with different combinations of surgical approach (CO and RW) and type of cochlear implant (LW and PM). Secondly, we want to investigate these treatment options by assessing the cone beam CT images postoperatively. Thirdly, we want to find ECochG outcome measures that reflect best the extent of insertion trauma by comparing these measures to the CT images and hearing test scores.

[figure not shown]

Figure 1: This is a schematic coronal plane of a cochlear duct. The cochlea consist of several compartments: scala vestibuli, scala media and scala tympani. The CI should reside in the scala tympani, herein laterally and medially for the LW and PM electrode array respectively. Translocation of the CI from scala tympani to the scala media or scala vestibuli (from downward to upward) damages vital structures like the basilar membrane with the organ of Corti or stria vascularis.

[figure not shown]

Figure 2: Cone beam CT scan. 'Cochlear view': position of the CI (the white dotted radiopaque curled line) can be easily assessed. The 16 electrodes of the CI are reflected by the white dots.

2. OBJECTIVES

Primary Objective:

To compare hearing preservation percentage after cochlear implantation between two surgical approaches (CO, RW) and two electrode array designs (LW, PM).

Secondary Objective(s):

- To determine the relationship of scalar position of the electrode array and hearing preservation (i.e. residual acoustic hearing).
- To determine the relationship of scalar position of the electrode array and hearing performance after one year with CI.
- To assess residual hearing over time after implantation.
- To find which ECochG measures can be used best for assessment of insertion trauma.
- To determine the relationship between ECochG measures and residual hearing and speech perception postoperatively.
- To determine the relationship between ECochG measures and scalar position of the electrode array.

3. STUDY DESIGN

The study design is illustrated in **figure 3**:

This study concerns a single-blind mono-center randomized controlled, with 18 year and older severely or profoundly hearing-impaired patients who are eligible for a cochlear implant. Every candidate for cochlear implantation needs to have severe hearing loss bilaterally, should not have contraindications for surgery and should be able to follow an intensive medical rehabilitation program. The study will be performed at the department of Otorhinolaryngology in the University Medical Center Utrecht, and will run till 01-01-2027.

[figure not shown]
All participants will undergo the usual standard medical care of work-up before cochlear implantation. The work-up includes a pure tone audiogram (PTA), a speech audiogram, a preoperative CT, and interviews with speech therapist, audiologist, ENT surgeon and social worker. In a multidisciplinary meeting, the Cochlear implantation team of the UMC Utrecht will assess all results and decides whether a patient is suited for a cochlear implant.

Eligible cochlear implant candidates will then for this study be randomized to group 1 (RW + LW), 2 (CO + LW), 3 (RW + PM) or group 4 (CO + PM).

Study procedures:

For all patients, during implantation, the standard measurements for eCAP and electrode impedances and the experimental measurements of ECochG will be performed. Postoperatively, a cone beam CT scan will be made to assess the scalar position of the CI. After activation of the CI, which is usually around three to four weeks postoperatively, the ECochG measurements will be repeated. For this study, we add two extra pure tone audiograms at 6 /12 months, resulting in a total of 4 audiograms (at one three, six and 12 months). Pure tone audiometry is without CI, which will allow us to determine the residual acoustic hearing capability of the patients. At 12 months, a conventional speech perception test with consonant-vowel-consonant (CVC) word score with/without noise will be performed. The speech perception test is with CI and determines the maximal electrical hearing capability of the patients. Finally, at 12 months, we will add a spectral ripple test, allowing us to measure hearing performance independent of cognitive and linguistic skills (Drennan et al., 2014).

Study Design

Light grey: Standard medical care

Dark grey: Extra for study

Figure 3. Flow chart study procedures. PTA: pure tone audiometry, CB-CT: conebeam CT, ECochG: Intracochlear electrocochleography, eCAP: Evoked compound action potential, CI: cochlear implant.

4. STUDY POPULATION

4.1 Population (base)

Subjects eligible for participation in the study are:

Patients with severe to profound bilateral hearing loss (thresholds >70 dB HL for 2-8 kHz) who were diagnosed and counselled by the Cochlear Implantation team of the UMC Utrecht, and willing to participate in this study.

4.2 Inclusion criteria

- 18 years of age or older
- normal function of middle ear (i.e. no acute middle ear infections)
- dutch language proficiency
- choice for Advanced Bionics implant

4.3 Exclusion criteria

- prior otologic surgery in the implanted ear (excluding tympanostomy tube placement)
- inner ear malformation present in the ear to be implanted (i.e. ossification, Mondini malformation)
- retrocochlear pathology present in the auditory system to be implanted
- neurocognitive disorders
- sudden deafness

4.4 Sample size calculation

Hearing preservation is the main outcome variable (see further 5.1). Based on literature (Manjaly et al., 2018; Rader et al., 2018; Sierra et al., 2019) we expect a large range of hearing preservation for each group, from 0 (no preservation, i.e., loss of all hearing) to 100 (full preservation, hearing stable), and occasionally above (improved hearing). The three studies showed means of 56, 74, and 53, respectively and within-group standard deviations, σ_w , of 37, 19 and 37. Weighing the larger studies more (Manjaly, Sierra) we estimate $\sigma_w = 35$ group means of 50 with clinically interesting differences of 40 between best and worst group means. This yields a variance between groups of 400, i.e., $\sigma_B = \sqrt{400} = 20$ (σ_B : standard deviation between groups). Thus, effect size $\sigma_B / \sigma_w = 0.57$. Using a group size of 12 yields a robust power of 0.9. We used G*power (version 3.1.9) to calculate the power based on effect size and sample size with a one-way ANOVA test, with fixed effects.

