5.2 Randomisation, blinding and treatment allocation

Patients will be randomly allocated to one of four groups. Block randomization will take place electronically by the study management system researchtool. The Julius Center will handle this randomization procedure. All groups carry the same equal weight. They will stratify the groups for age, with two subgroups, 18-50 years and > 50 years. This study is single-blind, meaning that only participants are blinded for the treatment allocation. However, research assistants will be blinded for the treatment.

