7. STATISTICAL ANALYSIS

7.1 Descriptive statistics

We will use an ANOVA test to compare the primary outcome measure hearing preservation (see 5.3) between the four groups. We will do the same for the CVC word score tests (with and without noise) between the groups.

Fisher's exact test of independence will be used to compare the electrode location within the scala tympani (correct location after insertion) between CO or RW approach, and between PM or LW electrode insertion.

We will also use multiple regression analysis to identify independent predictors of hearing preservation. Among the factors to examine are insertion depth and cochlear volume.

We will use a Pearson correlation test to examine the correlations between the ECochG responses and hearing preservation at the various time points (during and after cochlear implantation)..

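### Section 4.4 presents the largest between-group variance that a 40-point range allows as the one it yields, so the stated power of 0.9 is a ceiling: with 12 per group, power runs from 0.60 to 0.90

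*Protocol*

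**What the plan says.** Protocol section 4.4 sets out its assumptions in one chain. It starts with "we estimate $\sigma_w = 35$ group means of 50", adds "clinically interesting differences of 40 between best and worst group means. This yields a variance between groups of 400", takes the square root to get a between-group SD of 20, divides by 35 to get an effect size of 0.57, and concludes: "Using a group size of 12 yields a robust power of 0.9". The calculation is for a one-way fixed-effects ANOVA.

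The rest of the protocol matches that test. Under section 5.2, "Patients will be randomly allocated to one of four groups" and "All groups carry the same equal weight". The Summary gives a total of 48 patients. In section 7.1, "We will use an ANOVA test to compare the primary outcome measure hearing preservation", between the four groups.

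Neither section 4.4 nor any other part of the protocol gives the means of the two groups between the best and the worst. Section 4.4 does not state a significance level.

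**The concern.** The variance of four means depends on all four, not only on the largest and smallest. Section 4.4 fixes two of them and then gives a single variance as if it followed. If the figure used is the most favourable one compatible with the stated range, the quoted power is an upper limit presented as the expected value.

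This matters because 0.9 is the only justification given for 12 per group. The 40-point difference is the one the protocol itself calls clinically interesting. A reader of section 4.4 would believe that the primary test has a 10% chance of missing it, and could take a non-significant result as good evidence against a difference of that size.

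**Working it through.** **Inputs.** From section 4.4: within-group SD 35, average of the group means 50, best minus worst 40, n = 12 per group, one-way fixed-effects ANOVA. From section 5.2: four equally weighted groups, so k = 4 and N = 48. Assumed: α = 0.05.

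**Formulas.**
- Between-group variance: σ_B² = Σ(mean_i − overall mean)² / k. The divisor k = 4 is the one that gives the protocol's 400.
- Effect size: f = σ_B / 35.
- Noncentrality: λ = N·f² = 48·σ_B² / 35² = 48·σ_B² / 1225.
- Power: the probability that a noncentral F with 3 and 44 degrees of freedom and noncentrality λ exceeds the central 5% critical value, F = 2.816.

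**Reproducing the stated figure.** f = 20/35 = 0.571 and λ = 48 × 400 / 1225 = 15.67, giving power 0.903. With f rounded to 0.57, power is 0.902. The stated 0.9 is therefore reproduced, and the arithmetic from the variance onward is right. It also supports the assumed α: 0.025 would give 0.84 and 0.10 would give 0.95.

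**What a range of 40 allows.** Put the extremes at 30 and 70.
- Maximum: two groups at each end. Every mean is 20 from the centre, so σ_B² = 4 × 20² / 4 = 400.
- Minimum: both middle groups at the midpoint. σ_B² = (20² + 0 + 0 + 20²) / 4 = 200.

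A search over all positions of the two middle means gives power from 0.601 to 0.903, the same two end points.

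**Power by pattern** (every row has mean 50 and range 40):

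| Four means | σ_B² | f | Power, n = 12 |
|---|---|---|---|
| 30 / 30 / 70 / 70 | 400 | 0.571 | 0.90 |
| 30 / 32 / 68 / 70 | 362 | 0.544 | 0.87 |
| 30 / 35 / 65 / 70 | 312.5 | 0.505 | 0.81 |
| 80 / 40 / 40 / 40 | 300 | 0.495 | 0.79 |
| 30 / 40 / 60 / 70 | 250 | 0.452 | 0.71 |
| 30 / 43.3 / 56.7 / 70 | 222 | 0.426 | 0.65 |
| 30 / 50 / 50 / 70 | 200 | 0.404 | 0.60 |

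**Does another divisor rescue the step?** No. With k − 1 = 3, the variances are 533 for the two-and-two tie, 296 for even spacing and 267 for the midpoint pattern.

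**Variance needed.** Power of 0.90 requires f = 0.568, that is σ_B² = (0.568 × 35)² ≈ 396 out of a possible 400. Power of 0.80 requires about 304.

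**Range detectable with 0.9 power, n = 12.** Setting σ_B² = 395.5 and solving for the range R:
- two-and-two, σ_B² = R²/4: R = 39.8 points
- one group apart, σ_B² = 3R²/16: R = 45.9 points
- evenly spaced, σ_B² = 5R²/36: R = 53.4 points
- both middle groups at the midpoint, σ_B² = R²/8: R = 56.3 points

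**Group size for 0.9 power at a 40-point range.** 12, 16, 21 and 23 per group for the same four patterns, that is 48, 64, 84 and 92 patients.

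**What the patterns mean in this 2×2 design.** 30/30/70/70 arises if only the approach or only the electrode matters, or from a pure crossover interaction. 30/50/50/70 arises if approach and electrode each add 20 points. One group apart describes a single best combination.

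**The case against.** The strongest reply is that the section contains no wrong number. Means of 30/30/70/70 have average 50, range 40, variance 400, f = 0.57 and power 0.90, and such a pattern is natural in a 2×2 trial. The primary objective in section 2 is framed by approach and by electrode, and a 40-point effect of one factor alone gives exactly that tie. On this view the fault is an undeclared assumption rather than an error.

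It stands that the pattern is possible and that section 4.4 is internally correct under it. It does not stand that the range yields it: section 4.4 speaks of best and worst group means and names no pattern. The Summary's own expectation, "Our hypothesis is that the combination of a RW approach and a LW lying electrode array minimizes insertion trauma", reads more naturally as one best group than as an exact tie between two. It gives no means, however, and does not exclude a joint best, so it cannot settle the pattern either way.

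Two further points are fair. First, 0.60 is a bound, and nothing in the protocol makes it more likely than other values. Second, small departures from the tie cost little if 0.9 is read to one decimal: 30/32/68/70 still gives 0.87, and 0.85 needs a variance of about 343. The material loss comes with larger departures.

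A factor-level test would not remove the problem. Sections 4.4 and 7.1 both name a comparison of four groups. A 24 versus 24 main-effect comparison (error df 44) reaches 0.9 power at about 33.5 points but has only about 0.49 for the 20-point effect implied by 30/50/50/70.

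**Conclusion.** The concern holds. A 40-point range among four means gives a variance anywhere from 200 to 400, and section 4.4 takes the maximum and presents it as a consequence. Power of the planned four-group test with 12 per group is therefore 0.60 to 0.90. The chance of a non-significant result at the protocol's own clinically interesting difference is 10% at best and 40% at worst. The word robust is not supported, because 0.9 is the ceiling.

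The result rests on the protocol's SD of 35, 12 analysed patients in each group and α = 0.05. The last is an assumption, but it is the conventional level that reproduces the stated 0.9. That the variance lies between 200 and 400 depends on none of these. This should be fixed, but it does not by itself invalidate the design.

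**What to change.** Reword section 4.4:
- State the four assumed group means and the significance level, and report the power those means give.
- Say that a best-to-worst difference of 40 corresponds to f between 0.40 and 0.57, so that 12 per group gives power between 0.60 and 0.90 for the four-group ANOVA, depending on the middle groups.
- Remove the word robust.
- Give the range detectable with 0.9 power: about 40 points for a two-and-two tie, 46 for one best group and 56 if approach and electrode add equally.

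A main-effect power figure is optional. If one is added, quote both the 33.5-point and the 20-point results.

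The cost is a change of wording and a less favourable power statement. Sample size, test and endpoint can stay as they are if the sponsor accepts the restated power. If 0.9 is to be kept at a 40-point range under another pattern, the trial would need 64 patients (one best group), 84 (even spacing) or 92 (equal additive effects) instead of 48.
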